Approximately 1 of every 3 surgical procedures nationally is performed on a patient ≥ 65 years of age yet this demographic represents only 13% of the population.¹⁻³ At our institution, a tertiary care center, 40% of elective, non-cardiac surgery is performed on seniors (see Feasibility Data). This proportion will grow, as seniors (defined here and throughout as persons ≥ 65 years) are a fast-growing segment of the population. Making matters worse, geriatric surgical patients often do poorly.^{2,4-7} Thirty-day mortality for community dwelling Medicare enrollees is a remarkable 4.5% for appendectomy and 18% for colectomy and double this for nursing home residents, and even survivors frequently experience sustained functional decline.^{1,2,4} This places enormous emotional and economic burdens on geriatric patients, their families, and the healthcare system. The challenge therefore is to identify risk factors for poor outcomes preoperatively so that the vital organ function can be improved or accommodated in the planning and execution of surgical, anesthetic, and postoperative care. Preoperative assessment of vital organs—heart, lungs, kidney, liver, blood—has been a staple of preparation for surgery for decades, and established algorithms address how to evaluate and manage a wide range of conditions perioperatively. Oddly, the brain is not among the vital organs that get formally evaluated preoperatively.⁸ For geriatric surgical patients, this is a major and likely costly omission because brain dysfunction is common in seniors. Five-10% of Americans over age 65 and 25-40% of those over 85 have dementia; including MCI (mild cognitive impairment), the prevalence of cognitive impairment is 35-50% in those ≥ 65 (depending on the age structure of the population and the definition and assessment methods used) and higher still in those ≥ 85 .⁹⁻¹¹ Therefore, it is reasonable to assume that many seniors scheduled for elective surgery have cognitive impairment that goes unrecognized. Our preliminary data support that hypothesis. We preoperatively screened 289 geriatric elective surgical patients with the MiniCog, a brief and well-validated test of visuospatial representation, recall, and executive function,¹²⁻¹⁷ and found, using standard cutoffs, that 24% overall and 33% of those ≥ 75 years of age scored in a range that suggests functionally meaningful impairment. Yet, the intake nurse classified all but one as being cognitively intact, including 3 of 4 who had a MiniCog of 0. These results are consistent with published data from smaller studies that used similar tools to

screen patients ≥ 65 years presenting to an emergency department or having surgery with planned admission to the ICU which, depending upon the type of cognitive testing and age, show 20% to 63% are cognitively impaired.¹⁸⁻²¹ Thus, there is evidently a problem that goes undetected without screening.

But does it matter? We contend the answer is 'yes'⁸ and conceptualize cognitive impairment as a form of brain failure that, like heart failure, arises from multiple causes but leads independently to poor outcomes. Evidence supports this reasoning. First, cognitive dysfunction is a risk factor for adverse life events.²² At a minimum, therefore, cognitive screening may help identify those least likely to benefit from the surgery. Second, routine clinical interactions, whether in primary care or hospital settings, are insensitive for detecting cognitive impairment or even frank dementia,^{13,17,23} an observation we confirmed in our pilot study (Preliminary Data). Failure to recognize the problem could lead to suboptimal outcomes in a surgical setting if patients cannot recall what is expected of them postoperatively in terms of activity restrictions, wound care, medication regimens, and rehabilitation. Third, many seniors experience subtle and long-lasting executive dysfunction postoperatively that is independent of the specific anesthetic or surgical procedure, suggesting the patient's preoperative cognitive function is a predisposing factor.²⁴⁻²⁶ Fourth, some evidence indicates poor cognitive status increases complication risk, undermines the chance of a good outcome, and adds to the cost of care. In hospital delirium is a prime example, as it occurs in 15-80% of older surgical patients and contributes to poor outcomes.²⁷⁻³⁰ Although pre-existing cognitive impairment is an established risk factor for delirium, we seldom know a patient's cognitive status preoperatively because it is not currently assessed. Pre-existing cognitive impairment may also be a risk factor for serious non-cognitive morbidity^{31,32} or mortality in geriatric patients having major elective operations¹⁹⁻²¹ but data on non-cognitive outcomes are limited and no such association has been tested in a naturalistic, real-world setting (i.e. screening by regular preoperative evaluation center staff) such as we propose. Nonetheless, it is noteworthy that brief screening tests like the MiniCog were sufficient to detect such relationships and that guidelines issued jointly by the American College of Surgeons (ACS) and the American Geriatrics Society (AGS) strongly recommend routine preoperative cognitive assessment and specifically mention the MiniCog, detailed history, and informant questionnaire³—precisely the tools we propose to use. Still, perhaps because the data justifying the recommendation are sparse, it has not been widely adopted.

With national geriatric surgery volume large and growing and morbidity high, better understanding of preoperative cognition as a predictor / mediator of outcome has the potential to yield huge clinical and economic dividends. Assuming identification of a problem is the first step in solving it and that cognitive impairment is a form of brain failure, the lack of routine preoperative cognitive screening is presumably a major barrier to improving geriatric surgical care. Having demonstrated already in 289 patients that MiniCog testing is feasible in a preoperative evaluation center and that even non-medical personnel can administer and score it reliably (Preliminary Data), we are optimistic such screening can be implemented broadly. Unclear, however, is whether it is worth doing in terms of providing information about cognitive function that is unavailable from standard sources (patient/informant inquiry, focused chart review) and whether, like dysfunction of other vital organs, preoperative brain dysfunction is relevant to the surgical outcome of seniors.

Because of our success in screening older surgical patient undergoing elective surgical procedures we are now investigating whether the baseline peripheral immune status as measured by inflammatory cytokines in the plasma and white blood cell response to an ex-vivo immune challenge is predicted by the patient's baseline cognitive screening score. This will allow us to determine whether an exaggerated immune response to the surgery is predictive of adverse outcomes in aging patients.

The results of this work will lay the foundation for future studies that treat preoperative cognitive impairment as a risk factor and test interventions to improve geriatric surgical care and outcomes based on it. Examples might include discussion about the appropriateness or timing of surgery, preoperative consultation by a geriatrician, more careful titration of depth of general anesthesia (recently shown to reduce the risk of delirium),^{33,34} or triage to a specialized geriatric care unit postoperatively.^{31,35} Given the prevalence of likely cognitive impairment in our pilot study, preoperative cognitive screening promises to be an excellent low-cost, patient centered, high impact proposition for enhancing surgical outcomes in seniors.

Objectives:

Our overriding hypothesis is that preoperative cognitive impairment is a risk factor for poor surgical outcomes in seniors and that preoperative screening is superior to standard or systematic clinical processes for identifying at-risk patients.

Objective 1. Assess the marginal benefit of structured preoperative cognitive screening relative to standard or systematic preoperative evaluation for identifying seniors with likely cognitive impairment.

Objective 2. Determine whether preoperative cognitive impairment predicts postoperative outcome.

Objective 3. Determine whether other preoperative variables (mood, social support, history of depression, pain, and health and functional status) predict postoperative outcome.

Subject Selection: This project is designed as a prospective, single-center observational study. The cohort will consist of 500 consenting subjects \geq 70 years of age who present to the BWH Weiner Center for Preoperative Evaluation (CPE) prior to elective thoracic surgery (specifically, thoracoscopic lung resection, lobectomy, thoracotomy, or esophagectomy) or to neurological anterior, posterior cervical, thoraco, or lumbar spine surgery performed by neurosurgeons or orthopedic spine surgeons. 250 subjects undergoing thoracic surgery will be recruited and 500 subjects undergoing spine surgery will be recruited. These ages are chosen as significant clinical data demonstrate increased cognitive impairment in community dwelling elders. Eligibility criteria include: patients \geq 70 years of age with an ASA physical status of I-III presenting for elective thoracic, or orthopedic anterior or posterior cervical, thoraco, or lumbar spine surgery. Exclusion criteria will include history of stroke (not including TIAs) or brain tumor, uncorrected vision or hearing impairment (unable to see pictures or read or hear instructions); limited use of the dominant hand (limited ability to draw); and/or inability to speak, read, or understand English.

An additional cohort of 50 patients aged 45-60 undergoing elective neurological posterior thoracolumbar spine surgery or orthopedic spine surgery with an ASA physical status of I-III will be recruited through the BWH Weiner Center for Preoperative Evaluation (CPE). Eligibility and exclusion criteria will be the same as the aged 70 and older cohort, barring age. The purpose of enrolling this small younger subject population is to compare biomarkers between the two groups.

After obtaining consent, study staff will gain information about the patient's age and years of education. Study staff will administer standard instruments to assess mood (Geriatric Depression Scale-Short [GDS], a 15-item self-report questionnaire, and the Beck Anxiety Inventory [BAI]), The Amsterdam Preoperative Anxiety and Information Scale [APAIS], a brief, 6-item self-report questionnaire), social support (MOS Social Support Survey, a 12-item self-report questionnaire), pain (the Brief Pain Inventory Short-Form), frailty (the FRAIL scale assessing fatigue, resistance, ambulation, illness, and loss of weight), a risk assessment prior to surgery (MEDIA) measuring previous difficulties with memory, episodes of confusion, and cognitive enhancing medications, physical activity (the International Physical Activity Questionnaire – Short Form), and health and functional status (basic and instrumental activities of daily living [ADLs and IADLs, RAND 36-SF, and the WHODAS respectively]). The World Health Organization Disability Assessment Schedule 2.0 (WHODAS) is an alternative to the SF36 to measure physical health and disability. Past diagnosis of

depression and pain noted on the patient's preoperative evaluation form will be recorded, as well as past history of delirium or other post-anesthetic complications, use of hearing and/or hearing aids, and medical comorbidites. In addition, patients will be asked if they've had a fall within the last 6 months, whether they've been evaluated for a change in memory or thinking, who accompanied them to their appointment, their employment status and their living situation (alone, institutionalized, living with family members) in a patient survey. The study staff will also administer the MiniCog, a simple cognitive screening tool that takes just 2-4 min to complete and has little or no education, language, or race bias. In addition, the Animal Fluency test will be administered, which is a short cognitive screen that takes one minute to complete. Patients will also complete the self-report cognitive assessment CANTAB Insight Cognitive Exam, using an iPad developed by Cambridge Cognition. This 10 minute assessment measures cognitive health on five axes: executive function, processing speed, attention, working memory, and episodic memory through three cognitive tests: Matching Patterns, Working Memory, and Pairs Associates Learning Tests. Other measures of cognitive impairment will be obtained by study staff through: documentation on the patient's standard preoperative form, patient or informant report of diagnosis or evaluation for cognitive impairment or memory concerns, and systematic medical record review. Each enrolled patient will receive a business card listing the investigators' contact information and be advised to expect a follow up telephone call 6 months and 1 year after surgery to verify data elements and reassess functional outcome.

During their routine preoperative blood draw the phlebotomist will be provided with one 10mL heparinized blood tube, one 5mL heparinized blood tube and one 5mL non heparinized blood tube labeled with only the patient's study ID number that will be returned to the investigative team and processed within 30 minutes of the blood draw. If the phlebotomist is not able to obtain a sample during the patient's preoperative appointment, a sample will be drawn by a study staff member trained by one of the anesthesiologists, or a nursing or physician member of the anesthesiology team prior to incision instead. 200 μ L of this sample will be sent to a Partner's Core Facility for analysis of the APOE gene, specifically for the e4 allele which has been shown to be linked in the development of late-onset Alzheimer's and delirium. The presence of the E4 allele will be included in our multivariate analysis for the development of postoperative delirium. Genetic results will not be shared with participants, nor entered into the medical record. 20mL of blood will also be obtained on postoperative days 1-3 by a study staff member trained by one of the

anesthesiologists, or a nursing or physician member of the anesthesiology team. Total, the proposed collection is 80mL.

However, the additional 60mL blood sample on post-op days 1-3 will only be collected if the Hematocrit level is 0.25 or higher. Briefly, half of the sample would be spun down and plasma harvested and stored at -80 degrees C and when an adequate sample size obtained used to measure inflammatory cytokines by ELISA. From the whole blood, we will isolate and purify monocytes using magnetic activated cell sorting (MACS), and then further isolate total RNA from the monocytes, which will be analyzed using RNA-seq. This analysis will capture the complexity of monocytes at different stages of the perioperative state by providing a comprehensive, genome-wide sampling of cell types. The remainder of the sample will be divided into 1-ml aliquots and incubated at 37°C for 15 min with phosphate-buffered saline (PBS) (control), 100 ng/ml interleukin (IL)-6, 100 ng/ml IL-10, or a combination of 100 ng/ml IL-2 and 2 ng/ml granulocyte macrophage colony-stimulating factor, or 1g/ml lipopolysaccharide. Blood samples will be resuspended in 1.4 ml stabilizing buffer and incubated for 10 min at room temperature for fixation in PFA, cooled to 4C, and stored at 80C until further processing for flow cytometry to determine the immune response of the white blood cells to a ex-vivo immune challenge and whether these correlate with Mini-Cog score or the development of delirium. We will be sending de-identified (containing only subject ID and whether they were in the young or old cohort) blood samples from the proposed research to the Broad Institute and OLINK for RNA-seq analysis and protein analysis, respectively. We have fee-for-service agreements with both services. All samples and data collected for this research will be obtained with IRB approval and informed consent of study participants to sharing de-identified data. We will transfer de-identified blood samples of the patients enrolled in the study. We will then receive analyses in the form of raw data through PI-controlled password encrypted data files. The identities of research participants will not be disclosed to the repository. We will take appropriate steps to de-identify datasets according to the HIPAA privacy law. https://privacyruleandresearch.nih.gov/pr_08.asp. The raw data collected from the Broad Institute and OLINK will then be further analyzed by research staff listed on this protocol.

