Data Analysis: As in our pilot study, we will define "likely cognitive impairment" as a score ≤ 2 on the MiniCog; while we are aware it is by no means a gold standard, it is based on a well validated cutoff that serves our purpose of identifying patients who may need special approaches during the perioperative period. All analyses will be repeated in the subset of individuals with the greatest degree of cognitive impairment based upon a MiniCog score of (0-1) in order to understand why these individuals were not identified as cognitively impaired. We will first test the sensitivity of standard procedures compared to systematic procedures with MiniCog defined impairment or severe impairment. We will also compare sensitivity and specificity of the standard vs. systematic approach, and vs. the published sensitivity of 75% in comparable populations. As a secondary outcome, we will try to understand the full relationship among our four assessments, for instance whether systematic chart review and patient/informant reports detect individuals not detected by standard MiniCog cutoffs, as such individuals would be important to include as part of a broad "impairment" outcome for Aim 2 and consider in

subsequent work for special care in the perioperative period. Similarly, if we see patients who have received a formal evaluation of cognitive status in a memory clinic, by a primary care physician, or neuropsychological testing, we will try to understand qualitatively how MiniCog scores compare to such evaluations. Another secondary outcome will be how well patient/informant report can augment chart review when the patient does not have a primary care physician within our network. Differences between sensitivities and specificities will be compared using standard methods using confidence intervals.

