Information. Methods to reduce this risk include all investigators undergoing extensive training in general principles of informed consent, confidentiality, and administering research instruments in a humane, reliable, and valid manner. All data will be deposited into REDCap, a secure, web-based application for research storage and used for research purposes. There will be no interventions as a result of this study. The data gathered will have no effect on the care that the patient is to receive. Both the CPE providers preoperatively evaluating the patient and the surgeon will not have access to the result of the baseline testing.

Potential Benefits:

This study is being performed to advance medical knowledge. There are no expected benefits to individual subjects participating in the study but it will help advance understanding of how preoperative cognitive performance affects perioperative outcomes in older patients. This study has the potential to aid and improve decision-making by physicians and older patients in the future if they reveal a relationship between poor preoperative cognitive status and adverse cognitive and functional postoperative outcomes in older patients.

Monitoring and Quality Assurance:

Regardless of monitoring plans, the principal investigator is ultimately responsible for ensuring that the study is conducted at his/her investigative site in accordance with the IRB-approved protocol and applicable regulations and requirements of the IRB.

The Principal Investigator or a member of the investigative team will monitor each subject at this single site, and will review the accuracy and completeness of all testing, source documents and informed consent.

There will be no Data Safety Monitoring Board as the results of these studies will have no impact on the care that patients receive. The outcomes of the study are intended to be published in a peer-reviewed manuscript to document whether preoperative cognitive screening is a risk factor for adverse postoperative outcomes and the feasibility and cost of preoperative cognitive stratification in the preadmission testing center. All adverse events will be reported to the Partners the Human Research Committee (HRC) in accordance HRC guidelines. A 24-hour/7-day telephone or pager number will be provided for contacting the licensed physician investigator for this purpose.

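### Objective 1: one study staff group collects both the MiniCog reference and the systematic comparator with no stated order or masking, so the comparator's independence is not assured

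*Combined protocol and SAP*

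**What the plan says.** Study Procedures describes one staff-run session. It includes "a risk assessment prior to surgery (MEDIA) measuring previous difficulties with memory, episodes of confusion, and cognitive enhancing medications", and a survey that asks patients "whether they've been evaluated for a change in memory or thinking". It then states "The study staff will also administer the MiniCog", followed by Animal Fluency and CANTAB. Next comes "Other measures of cognitive impairment will be obtained by study staff through" three sources: the standard preoperative form, what the patient or an informant reports, and a systematic review of the record.

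Data Analysis makes the MiniCog (score of 2 or less, with 0–1 as the severe subset) the reference: "We will first test the sensitivity of standard procedures compared to systematic procedures with MiniCog defined impairment". Differences in sensitivity and specificity are to be compared through confidence intervals.

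The one masking statement is under Risks and Discomforts: "Both the CPE providers preoperatively evaluating the patient and the surgeon will not have access to the result of the baseline testing". Nothing is said about masking within the study staff or about the order of the measures.

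**The concern.** A sensitivity estimate is credible when the comparator is read without knowledge of the reference. Here the systematic comparator involves judgement. Memory concerns count alongside formal diagnoses, and no rule says what makes a chart or an answer positive. Someone who knows that a patient scored 0 may probe further or read an equivocal note as impairment. That raises agreement with the MiniCog.

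This bears on the main Objective 1 question, the marginal benefit of screening. In the pilot described in the introduction, 24% of 289 patients, about 69, scored as impaired, and the intake nurse classified all but one as intact. Routine detection was thus close to 1 in 69. The informative comparison is what the MiniCog adds over a systematic search, and that is the comparator most open to review bias. Such bias does not shrink with more patients and does not show in a confidence interval.

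**Working it through.** **Step 1: who handles what.** The plan does not define systematic procedures in one place. I take them to be the record review and patient/informant report that Data Analysis names. The introduction lists patient/informant inquiry among standard sources; if it belongs there, the label changes but the exposure does not.

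| Measure | Role | Handled by | Stated masking |
|---|---|---|---|
| MiniCog | Reference | Study staff | None to history or chart |
| Memory history, patient/informant report | Systematic comparator | Study staff | None to MiniCog |
| Record review | Systematic comparator | Study staff | None to MiniCog |
| Standard preoperative form | Standard comparator | Written by center providers, extracted by study staff | Writers masked; extractors not |

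The exposure is uneven. For the systematic comparator both content and coding are open. For the standard form only the extraction is.

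**Step 2: scale of sampling error.** The plan gives no sample-size or precision figure for Objective 1, so there is none to reproduce. Inputs:
- Older cohort N: 500 or 750 (Subject Selection gives both; used as a range).
- Prevalence of MiniCog impairment p: 24% (pilot, introduction).
- Systematic sensitivity s: 30% (assumption).

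MiniCog-positive patients, m = N × p:
- 500 × 0.24 = 120
- 750 × 0.24 = 180

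95% half-width, h = 1.96 × √(s(1 − s)/m):
- m = 120: 1.96 × √(0.21/120) = 8.2 points
- m = 180: 1.96 × √(0.21/180) = 6.7 points

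**Step 3: scale of possible bias.** If a share r of all MiniCog-positive patients moves from negative to positive on the systematic comparator, observed sensitivity becomes s + r by definition. The documents give no value for r.
- r = 5%: 30% becomes 35%. The shift is below both half-widths.
- r = 10%: 30% becomes 40%. The shift is above both.

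The shift equals sampling error at r = h, which is about 10 of 120 patients (0.082 × 120 = 9.8) or 12 of 180 (0.067 × 180 = 12.1).

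**Step 4: dependence on the assumptions.** Taking s as 30%, 50% or 75% and p as 24% or 33% (the pilot figure for age 75 and over), the half-width runs from 5.4 points (N = 750, p = 33%, s = 75%) to 8.9 points (N = 500, p = 24%, s = 50%). A 5-point shift is below all of these and a 10-point shift is above all of them.

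The bias can also be expressed as a share q of the patients whom systematic evaluation missed. The shift is then (1 − s) × q. With s from 20% to 50% and q from 5% to 20%, both assumed, it runs from 0.50 × 0.05 = 2.5 points to 0.80 × 0.20 = 16 points.

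**The case against.** The strongest reply is that the room for bias is limited and its direction is conservative. The form and chart are written records. Some report items, such as a prior diagnosis, are factual. The MiniCog has a fixed cutoff, and the introduction reports that non-medical personnel score it reliably. If systematic evaluation is flattered, screening looks less useful, so a finding that screening is superior would survive. Data Analysis also concedes that the MiniCog is not a gold standard and plans to study how the four assessments relate.

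Much of this stands. It limits the likely size of the bias and protects a positive conclusion. It does not protect the estimate of how much screening adds, and reliable scoring is not masking.

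A reader might infer more than the text supports:
- **That one person does everything for a patient.** The plan names a staff group. It neither requires nor prevents this.
- **That there is no masking at all.** The center's providers are masked, which protects the content of the standard form.
- **That several routes add up.** Stricter clock scoring needs the history to be heard before the test; an informant influenced by the test needs the reverse. Both cannot act through the same answer. The text describes the MEDIA and survey items before the MiniCog, though only as narrative order.
- **That the standard comparator is wholly untouched.** Study staff extract it too, and a history that affects MiniCog scoring may also be on the form.

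**Conclusion.** The point holds in limited form. As written, the plan lets knowledge of the MiniCog score enter the systematic comparator, and its confidence intervals would not reveal it. The supported conclusion is that independence is not assured. The documents do not show that it is absent.

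The likely direction is towards overstated systematic sensitivity and an understated marginal benefit of screening. The size is unknown. Against a half-width of 6.7 to 8.2 points (30% sensitivity assumed, pilot prevalence, 500 to 750 patients), reclassifying about 5% of MiniCog-positive patients would matter less than sampling error, and 10% or more would matter more. A 10-point shift should not be read as an expected value; it restates the assumption that 10% are reclassified. The change is worth making because it is cheap and because data already abstracted unmasked can be made independent only by abstracting them again.

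**What to change.** In Study Procedures, state the following:

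1. Patient and informant memory answers (MEDIA, prior evaluation, memory concerns) are recorded and locked in REDCap before the MiniCog is given.
2. The preoperative form and chart are abstracted by an existing staff member who did not test that patient, with the MiniCog, Animal Fluency and CANTAB fields hidden.
3. A positive record is defined in advance, separately for the form, the chart and the reported history.

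The plan should also reconcile who does the screening. The introduction describes testing by the center's regular staff, while Study Procedures assigns it to study staff; the answer determines who could be unmasked.

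The cost is some scheduling and REDCap permission work, with no added visit, patient or instrument. One gap remains: with the history taken first, whoever scores the MiniCog may still know it. That should be reported as a limitation; a second clock rater would be an added assessor and is not needed for this purpose.
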